Appendix 2. Schedule of Assessments

	Screen	Baseline/ Day 1 ^a	On-Treatment Study Week (± 3 Days)								Posttreatment Study Week (± 5 Days)		
			1	2	4	8	12	16 ^b	20 ^b	24 ^b	ET	4 ^c	12 ^c
Clinical Assessments													
Informed Consent		X											
Determine Eligibility	X	X											
Medical History	X												
Historical Resistance Test Data ^d	X												
Physical Examination	X	X					X ^e			X ^e	X		
Height	X												
Weight	X	X											
Vital Signs	X	X	X	X	X	X	X	X	X	X	X	X	X
12-Lead ECG	X												
Imaging for HCC ^f	X												
Adverse Events	X	X	X	X	X	X	X	X	X	X	X	X	
Concomitant Medications	X	X	X	X	X	X	X	X	X	X	X	X	
Pregnancy Prevention Counseling		X	X	X	X	X	X	X	X	X	X	X	X
Health Related Quality of Life Surveys		X			X		X			X	X	X	X
Study Drug Dispensing		X ^g			X	X	X ^h	X ^h	X ^h				
Review of Study Medication Adherence (Pill Count)			X	X	X	X	X	X	X	X	X		

				On-Treatment Study Week (± 3 Days)								Posttreatment Study Week (± 5 Days)			
		Screen	Baseline/ Day 1 ^a	1	2	4	8	12	16 ^b	20 ^b	24 ^b	ET	4 ^c	12 ^c	24
Laboratory Assessments															
Hematology, Chemistry	X	X	X	X	X	X	X	X	X	X	X	X	X		
Coagulation Tests	X	X					X			X	X				
HCV RNA	X	X	X	X	X	X	X	X	X	X	X	X	X	X	
Viral Sequencing/phenotyping ⁱ		X	X	X	X	X	X	X	X	X	X	X	X	X	
Pregnancy Testing ^j	X	X			X	X	X	X	X	X	X	X ^k	X ^k	X ^k	
Urinalysis & Urine Drug Screen	X														
HCV Genotyping, IL28B	X														
HCV, HIV, HBV Serology	X														
TSH, HbA1c, Fibrotest [®] /APRI	X														
Future Research Blood Sample ^l		X					X			X	X				

a Baseline/Day 1 assessments must be performed prior to dosing

b On-Treatment Visits at Weeks 16, 20 and 24 are only applicable to subjects in study group 4

c All subjects will complete the posttreatment Week 4 and Week 12 visits ; subjects with HCV RNA < LLOQ at the posttreatment (PT) Week 12 visit will complete the PT Week 24 visit

d Collect and record information regarding historical resistance test data if available

e A physical exam will be performed at the end of treatment visit (Week 12 for study groups 1,2,3; and Week 24 for study group 4)

f Liver imaging within 6 months prior to Baseline/Day 1 is required in subjects with cirrhosis to exclude HCC

g The IWRS will provide randomization to study Group

h Study drug dispensing at Week 12, 16 and 20 is only applicable to study group 4

i Plasma samples will be collected and stored for potential HCV sequencing/phenotyping and other virology studies.

j For females of childbearing potential only: serum β -hCG at Screening, urine test thereafter. If urine is positive, confirm immediately with serum β -hCG

- k Females of childbearing potential in study Groups 2 & 3 will have additional urine pregnancy testing every 4 weeks for a minimum of 6 months following last dose of RBV. If required by local regulations, additional pregnancy tests beyond 6 months may be added. In the event of a positive urine pregnancy result, subjects will be instructed to return to the clinic as soon as possible for a serum pregnancy test. Pregnancy test kits will be dispensed to female subjects of childbearing potential at the 4 and 12 Week posttreatment visits to self-monitor for pregnancy. The subject will be contacted by telephone monthly to confirm that urine pregnancy testing has been performed posttreatment and to record the outcome. Alternatively, if required by local regulations or preferred by the investigator or subject, the subject may return to the clinic for urine pregnancy tests.
- l Sample for optional future research will be collected at the Baseline/Day 1 visit and at the end of treatment (Week 12 for study groups 1,2,3; and Week 24 for study group 4) for subjects who have not opted out

Appendix 3. QOL Score Calculation Algorithms

CLDQ – HCV

CLDQ-HCV scores are calculated using subject responses to 29 questions in the questionnaire. If R_i is the score for the patient's response to the item i , for $i=1, 2, \dots, 29$ then the 4 domain scores are calculated as follows:

- Activity/Energy (AE) = Mean of $\{R_1, R_3, R_4, R_5, R_7, R_{18}\}$
- Emotion (EM) = Mean of $\{R_6, R_8, R_9, R_{11}, R_{16}, R_{23}, R_{24}, R_{27}, R_{28}\}$
- Worry (WO) = Mean of $\{R_{14}, R_{15}, R_{17}, R_{19}, R_{20}, R_{21}, R_{22}, R_{29}\}$
- Systemic (SY) = Mean of $\{R_2, R_{10}, R_{12}, R_{13}, R_{25}, R_{26}\}$

Here "Mean" is the average of nonmissing items (SAS mean function). Each score is calculated only if at least half of corresponding items are not missing. Otherwise, the score will be missing.

Over all CLDQ-HCV score is calculated by taking the mean of 4 domain scores {AE, EM, WO, SY}.

FACIT-F

Patient responses to 40 questions in FACIT-F questionnaire are rated in 0-4 score.

If less than 50% of responses in the corresponding domain are missing, the subscales for five domains are calculated as follows:

- Physical WEL
- l-Being (PWB) = $7 \times$ Mean of {GP1-GP7}
- Social/Family Well-Being (SWB) = $7 \times$ Mean of {GS1-GS7}
- Emotional Well-Being (EWB) = $6 \times$ Mean of {GE1-GE6}
- Functional Well-Being (FWB) = $7 \times$ Mean of {GF1-GF7}
- Fatigue Subscale (FS) = $13 \times$ Mean of {HI7, HI12, An1-An5, An7, An8 An12, An14-An16}

and

- FACIT-F Trial Outcome Index (TOI) = PWB+FWB+FS

If less than 20% of all 40 questions are not missing,

- TACIT-F Total Score = PWB+SWB+EWB+FWB+FS

WAPI: Hepatitis C

The response to Question 1 of this questionnaire provides the binary endpoint whether or not the subject had been in a paid employment during the week prior to assessment.

If the subject had been in a paid employment (Response to Q1 is “Yes”) at the visit when questionnaire was given, then following three scores are derived:

- Percent work time missed due to hepatitis C = $100 \times Q2 / (Q2 + Q4)$
- Percent impairment while working due to hepatitis C = $100 \times Q5 / 10$
- Percent overall work impairment due to hepatitis C =

$$100 \times \left[\frac{Q2}{(Q2 + Q4)} + \left(1 - \frac{Q2}{(Q2 + Q4)} \right) \times \frac{Q5}{10} \right]$$

Question 6 is applicable to all subjects:

- Percent activity impairment due to hepatitis C = $100 \times Q6 / 10$.
-

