15.11.6.1.5	Hemoglobin (g/dL) and Change from Baseline by Visit	Safety Analysis Set
15.11.6.1.6	Subjects with Postbaseline Hemoglobin < 10 g/dL and < 8.5 g/dL	Safety Analysis Set
15.11.6.1.7	Reticulocytes (x 10 ³ /uL) and Change from Baseline by Visit	Safety Analysis Set
15.11.6.1.8	WBC (x 10 ³ /uL) and Change from Baseline by Visit	Safety Analysis Set
15.11.6.1.9	Neutrophils (x 10 ³ /uL) and Change from Baseline by Visit	Safety Analysis Set
15.11.6.1.10	Lymphocytes (x 10 ³ /uL) and Change from Baseline by Visit	Safety Analysis Set
15.11.6.1.11	Platelets (x 10 ³ /uL) and Change from Baseline by Visit	Safety Analysis Set
15.11.6.1.12	INR and Change from Baseline by Visit	Safety Analysis Set
15.11.6.2	Treatment-Emergent Graded Laboratory Abnormalities	Safety Analysis Set
15.11.6.3	Treatment-Emergent Grade 3 or Above Laboratory Abnormalities	Safety Analysis Set
15.11.7.1	Systolic Blood Pressure (mmHg) and Change from Baseline by Visit	Safety Analysis Set
15.11.7.2	Diastolic Blood Pressure (mmHg) and Change from Baseline by Visit	Safety Analysis Set
15.11.7.3	Pulse (bpm) and Change from Baseline by Visit	Safety Analysis Set
15.11.7.4	Concomitant Medications	Safety Analysis Set
15.11.7.5	Summary of 12-Lead ECG Assessment at Baseline	Safety Analysis Set
15.12.1.1	Summary of SF-36 Quality of Life Questionnaire	Full Analysis Set by Randomized Treatment

Table Number	Title	Analysis Set
15.12.1.2	Summary of SF-36 Quality of Life Questionnaire	Full Analysis Set by Actual Treatment
15.12.2.1	Summary of CLDQ-HCV Quality of Life Questionnaire	Full Analysis Set by Randomized Treatment
15.12.2.2	Summary of CLDQ-HCV Quality of Life Questionnaire	Full Analysis Set by Actual Treatment
15.12.3.1	Summary of FACIT-F Quality of Life Questionnaire	Full Analysis Set by Randomized Treatment
15.12.3.2	Summary of FACIT-F Quality of Life Questionnaire	Full Analysis Set by Actual Treatment
15.12.4.1	Summary of WPAI: Hep C Quality of Life Questionnaire	Full Analysis Set by Randomized Treatment
15.12.4.2	Summary of WPAI: Hep C Quality of Life Questionnaire	Full Analysis Set by Actual Treatment

Figure Number	Title	Analysis Set
15.8.1	Subject Disposition	Screened Subjects-by Randomized Treatment Group
15.8.2	Subject Disposition	Screened Subjects-by Actual Treatment Group
15.9.1	Proportion of Subjects with HCV RNA < LLOQ While on Treatment by Visit	Full Analysis Set by Randomized Treatment Group

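### The FACIT-F total-score condition is inverted: followed as written, no subject can ever receive a total

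*SAP*

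**What the plan says.** SAP Appendix 3 (QOL Score Calculation Algorithms) holds the SAP's only scoring rules for the FACIT-F. It sets out the following:

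- The questionnaire: "Patient responses to 40 questions in FACIT-F questionnaire are rated in 0-4 score".
- The subscale condition: "If less than 50% of responses in the corresponding domain are missing, the subscales for five domains are calculated as follows". The five domains are physical, social/family, emotional and functional well-being (PWB, SWB, EWB, FWB) and fatigue (FS).
- The Trial Outcome Index (TOI), which is PWB + FWB + FS. It is listed before the total-score condition.
- The total-score condition: "If less than 20% of all 40 questions are not missing". Under it, the total is PWB + SWB + EWB + FWB + FS.

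The scores feed Tables 15.12.3.1 and 15.12.3.2, both titled "Summary of FACIT-F Quality of Life Questionnaire" in Appendix 1, and Figures 15.11.3.1 and 15.11.3.2. Section 3.6.1 deals with quality-of-life data missing at a visit. It gives no item-level rule and does not correct the condition.

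**The concern.** A completeness condition should admit questionnaires with enough answers and reject those with too few. The total-score condition does the reverse: it limits the share of items that *are* answered to below 20%. It runs against the FACIT-F subscale rule just above it, and against the CLDQ-HCV rule in the same appendix, which asks for at least half the items of a domain to be answered.

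A program or an independent check written to this text returns no FACIT-F totals. The carry-forward at posttreatment Week 24 in Section 3.6.1 would then have no total to carry. A program written to the presumed intention does produce totals, but departs from the SAP without saying so.

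**Working it through.** **Inputs (all from Appendix 3).** Item counts per domain:

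| Subscale | Source | Items |
|---|---|---|
| PWB | "Mean of {GP1-GP7"} | 7 |
| SWB | "Mean of {GS1-GS7"} | 7 |
| EWB | "Mean of {GE1-GE6"} | 6 |
| FWB | "Mean of {GF1-GF7"} | 7 |
| FS | HI7 and HI12 (2), An1 to An5 (5), An7, An8 and An12 (3), An14 to An16 (3) | 13 |

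Sum: 7 + 7 + 6 + 7 + 13 = 40, which reproduces the SAP's stated number of questions.

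**Step 1: answers needed for all five subscales.** A subscale with *n* items exists if missing/*n* < 0.50.

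- *n* = 7: at most 3 missing (3/7 = 43%), so at least 4 answered.
- *n* = 6: at most 2 missing (2/6 = 33%; 3/6 is exactly 50% and fails), so at least 4 answered.
- *n* = 13: at most 6 missing (6/13 = 46%), so at least 7 answered.

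The minimum for all five is 4 + 4 + 4 + 4 + 7 = 23 answers, or 23/40 = 57.5%.

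**Step 2: answers allowed by the total-score rule as written.** Answered/40 < 0.20 means answered < 8, so at most 7.

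**Step 3: both together.** The total is a sum of five subscales, so it needs at least 23 answers, while its own condition allows at most 7. No questionnaire satisfies both.

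A full enumeration agrees. There are 8 × 8 × 7 × 8 × 14 = 50,176 combinations of answered-item counts across the five domains. All five subscales exist in 4 × 4 × 3 × 4 × 7 = 1,344 of them, and the total-score condition as written is also met in 0.

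**Sensitivity.** If the subscale rule is relaxed to allow exactly 50% missing, EWB needs 3 answers and the minimum falls to 22. This is still above 7.

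**Step 4: the rule with *not* removed.** Missing/40 < 0.20 means missing < 8, so at most 7 missing and at least 33 answered. Then 500 of the 1,344 combinations qualify, including the fully completed form. These are counts of possible patterns, not proportions of subjects; the SAP gives no data on how many items subjects left blank.

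**The case against.** The case for giving this little weight has four parts.

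- **It is evidently a slip.** The intended direction can be read from the neighbouring rules, and the same appendix misspells the names of two instruments. A programmer who saw every complete form return a missing total would probably notice. This stands as a comment on likelihood: the loss is certain only under literal programming. It does not make the rule usable as written.
- **One step is inferred.** The FACIT-F text has no sentence setting the score to missing otherwise; only the CLDQ-HCV text has one. Taken alone, the total-score condition would admit nearly empty forms. That no total can ever exist follows only because a sum containing an undefined subscale has no value. The inference is sound, but the text should say it.
- **Most of the output survives.** The five subscales and the TOI are not governed by the inverted condition, so the FACIT-F tables would not be empty. Quality of life is not among the primary or secondary objectives in Section 1.1, nor among the secondary endpoints in Section 6.2.1, and Section 6.4.2 puts the analysis set at 82 subjects. This stands and limits the importance of the point.
- **The cut-off depends on the wording chosen.** Deleting *not* gives at least 33 answers. If the author meant at least 80% answered, the cut-off is 32 (32/40 = 80%). The value 33 follows from the SAP's own strict inequality, but the sponsor should confirm it.

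**Conclusion.** The concern holds. The FACIT-F total-score condition is inverted and cannot be met together with the subscale rule in the same appendix: at most 7 answers allowed, at least 23 required. Followed as written, every FACIT-F total is lost at every visit, including those from complete questionnaires.

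This rests on two readings: that the condition is programmed literally, and that a sum with an undefined component is itself undefined. The effect is confined to one descriptive composite score and leaves the efficacy and safety conclusions untouched. It should be corrected because it is an operative scoring rule, but it is not a major defect.

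**What to change.** In Appendix 3, restate the condition in terms of missing items, for example: the FACIT-F total is the sum of PWB, SWB, EWB, FWB and FS when fewer than 20% of the 40 items are missing (at least 33 answered) and all five subscales are derivable; otherwise it is missing.

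The derivability clause is needed because 7 missing items could all fall in one 7-item domain and leave that subscale undefined. The sponsor should confirm the boundary (33, or 32 if exactly 20% missing is acceptable).

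The cost is one line of text and a matching check in the scoring program and its independent verification. If the SAP is already final, the correction can be recorded in the clinical study report, as Section 1 provides for later changes. No data collection or other analysis is affected.
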